6.3.1 Patient characteristics and withdrawals

The total number of patients in the dietary lead-in safety population will be stated together with a summary of basic demographic data and data for other characteristics, including lipids. Patients withdrawn during the dietary lead-in period will be identified as screening failures and numbers will be stated. Similarly, the total number of patients in the randomised safety population will be stated together with a summary of demographic data and data for other characteristics, including pre-treatment lipids, by treatment group. The numbers of patients withdrawn at each visit and reasons for withdrawal will also be summarised by treatment group.

6.4 Method of statistical analysis

The primary analysis will be made on LDL-C as the LOCF in the ITT population. A supportive analysis will be made on the completer ITT population.

Lipids and lipoproteins (as part of the secondary objectives) are: TC, LDL-C, HDL-C, TG, ApoA-I, ApoB, nonHDL-C, ApoB/ApoA-I, TC/HDL-C, LDL-C/HDL-C, nonHDL-C/HDL-C and hs-CRP. Baseline for calculating percentage change in a lipid or lipoprotein will be the mean of values from Visits 2 and 3 (Weeks -2 and 0). Monotherapy will be assessed as the mean of Visits 4 and 5 (Weeks 4 and 6), and combination therapy will be assessed as the mean of Visits 6 and 7 (Weeks 10 and 12).

The effect of combination therapy will be assessed by analysis of co-variance (ANCOVA) using geometric percentage change, where the response variable is the logarithm of the ratio of the treatment value divided by the corresponding baseline value, and treatment and centre are the explanatory variables. Estimates of treatment effect, and their 95% CI, will be exponentiated to produce estimates of percentage change. For comparison with other studies, point estimates and confidence intervals will also be calculated arithmetically on the percentage change from baseline. However, the p-values for specified comparisons will be calculated for the geometric analysis only.

The estimates of the additional effects on lipids and lipoproteins of adding ezetimibe 10 mg to rosuvastatin 10 mg or 20 mg will be calculated in the same way using the geometric mean of the 2 monotherapy visits as baseline. Corresponding 95% CIs will be computed.

Depending on the distribution of patients across centres, it may be sensible to pool some small centres together by region. This will be discussed and agreed by biostatistical personnel and the clinical team at AstraZeneca before database lock.

The numbers and percentages of patients reaching appropriate goals will be summarised. Since the prescribed goals may change over time, the goals used in the evaluation will represent the current regional guidelines for this patient population at the time when the SAP is finalised (prior to database lock).

Formal analysis will be by logistic regression with terms for baseline LDL-C, centre and treatment in the model. Hypothesis testing in logistic regression models will be performed using likelihood ratio tests.

Analysis of hs-CRP will be performed using the non-parametric Kruskal-Wallis test (Hollander and Wolfe 1973). The median score will be used. In the case of pairwise comparisons, a Wilcoxon test will be used.

Lipid data will be analysed geometrically (log transformed). This transformation is preferred for the following reasons:

- Experience with similar data in the EXPLORER study shows that the change in LDL-C data has a rightward skew that increases in severity with increasing treatment efficacy
- A study of STELLAR data found that the arithmetic mean of percentage change from baseline produced estimates of efficacy that were consistently below the median effect. The geometric mean was much closer to the median
- Information collated from other studies suggests that ezetimibe has a multiplicative effect on LDL-C. This effect is better modelled by a geometric analysis
- A Bootstrap analysis of EXPLORER data showed that use of the geometric analysis provided equivalent power to the percentage change from baseline analysis with approximately 30% fewer subjects

AEs can occur in the dietary lead-in phase and the randomised phase of the study. All AEs will be classified according to the following:

- Treatment emergent. This is further categorised as:
 - Ongoing from the dietary lead-in period and subsequently worsening during the randomised period, and;
 - Starting during the randomised period

All AEs will be categorised by body system and MedDRA preferred term and listed for each patient. In the randomised safety population, treatment emergent events will be reported as frequencies in each treatment group. Frequencies of AEs leading to withdrawal from the randomised period will also be tabulated and reported by treatment group. AEs leading to death, SAEs and drug-related AEs and SAEs will be presented similarly. Tests of statistical significance will not be performed.

Haematology and clinical chemistry data will be listed for each patient and summarised for each treatment group at each visit. Values outside laboratory reference ranges will be highlighted.

Shift tables for haematuria and proteinuria data will show numbers and percentages of patients with categories of urinary protein and blood (none, trace, +, ++, +++ and ++++) at Week 12 against baseline (Week 0) and Visit 5 (Week 6).

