6. STATISTICAL METHODS AND DETERMINATION OF SAMPLE SIZE

6.1 Statistical evaluation – general aspects

A comprehensive statistical analysis plan (SAP) will be prepared before unblinding of the data, and before database lock.

Experience in previous studies indicates that within-patient fluctuations in LDL-C exhibit autocorrelations lasting a period of several weeks. Thus, overall precision will be increased by using an average of 2 measurements taken at least 2 weeks apart. Since the onset of lipid-lowering treatments is largely complete by 4 weeks, an average of measurements made at 4 and 6 weeks will provide an accurate estimate of the treatment effect throughout this period. In this study, all baseline and on-treatment effects are assessed as the mean of 2

consecutive measurements made 2 weeks apart. For reporting purposes, the average of weeks 4 and 6 is termed the effect after 6 weeks of treatment.

Two-sided tests of statistical significance will be used throughout.

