6.2 Description of outcome variables in relation to objectives and hypotheses

Primary outcome variable:

- Percentage LDL-C change from baseline to 6 weeks (mean of weeks 4 and 6) of combination therapy
- Statistical significance of the following 3 comparisons will be tested simultaneously by a Hochberg procedure to control for multiple comparisons:
 - 1. Rosuvastatin 20 mg + ezetimibe 10mg vs simvastatin 40 mg+ 10 mg ezetimibe
 - 2. Rosuvastatin 10 mg + ezetimibe 10mg vs simvastatin 40 mg+ 10 mg ezetimibe
 - 3. Rosuvastatin 20 mg + ezetimibe 10mg vs simvastatin 80 mg+ 10 mg ezetimibe

Secondary outcome variables:

The secondary outcome variables include:

- LDL-C, HDL-C, TC, TG, nonHDL-C, ApoB, ApoA-I, TC/HDL-C, LDL-C/HDL-C, nonHDL-C/HDL-C and ApoB/ApoA-I, hs-CRP; and the corresponding measures of effects are the respective changes from baseline
- Therapeutic lipid goals as described in American and European guidelines, with the corresponding measures of effect being the proportions of patients achieving goal

Exploratory

• Change in biomarkers (sitosterol, lanosterol, C4 and LpPLA2). An additional sample will also be drawn for possible other biomarkers and lipid fractions that are related to atherosclerosis

Clinical Study Protocol Drug Substance Rosuvastatin Study Code D356FC00003 Date

Safety

- AEs
- Vital signs (blood pressure and pulse rate)
- Clinical chemistry
- Haematology
- Urinalysis

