6.5 Determination of sample size

The size of the study population is based upon the primary endpoint, the percentage reduction in LDL-C after 4 to 6 weeks of combination therapy, and the following treatment comparisons:

- rosuvastatin 10 mg plus ezetimibe 10 mg vs simvastatin 40 mg plus ezetimibe 10 mg
- rosuvastatin 20 mg plus ezetimibe 10 mg vs simvastatin 40 mg plus ezetimibe 10 mg
- rosuvastatin 20 mg plus ezetimibe 10 mg vs simvastatin 80 mg plus ezetimibe 10 mg

These endpoints will be tested sequentially using the Hochberg procedure.

Power is calculated for simultaneously attaining all 3 endpoints. Since the success of the rosuvastatin 20 mg plus ezetimibe 10 mg vs simvastatin 40 mg plus ezetimibe 10 mg is essentially assured when the other 2 comparisons are met, the power calculation is based on those contrasts. In order for the overall power of the study to be 90%, each of the 2 contrasts must have approximately 95% power.

The rosuvastatin/ezetimibe combinations in this study have not been previously studied in large populations and so the effect size of these treatments is not known with certainty. Based

on the relative potencies observed for rosuvastatin and simvastatin monotherapies, and the approximately uniform supplemental effect of ezetimibe used with various statins, it is reasonable to assume an effect size of approximately 5% for the 2 comparisons between the rosuvastatin and simvastatin combinations, with a standard deviation (SD) of mean percentage reduction of 13%. This SD assumes a variance reduction because of the use of averages of replicates. Under these assumptions, a sample size of 177 ITT patients per arm is required.

Further exploratory calculations, based on logarithmic analysis and incorporation of an apparent increase in variation with increasing lipid-lowering effect, supported this conclusion.

It is anticipated that there will be a screen-failure rate of up to approximately 65% during the dietary lead-in phase and a dropout rate of 10% following randomisation.

Using this information, approximately 2285 patients will enter into the dietary lead-in phase, of whom 800 (approximately 200 per arm) will be randomised to receive study treatment.

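### The primary log-ratio ANCOVA, as ordinarily fitted, pools one residual variance over four arms, although Section 6.5 reports variation that appears to rise with lipid lowering; two of the three primary contrasts would then have modestly wrong standard errors

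*Protocol*

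**What the plan says.** Section 6.4 specifies the primary analysis: combination therapy is "assessed by analysis of co-variance (ANCOVA) using geometric percentage change, where the response variable is the logarithm of the ratio" of the treatment value to baseline, with treatment and centre as explanatory variables. From the same model, "Estimates of treatment effect, and their 95% CI, will be exponentiated to produce estimates of percentage change". P-values come from the log-scale analysis only. Section 6.4 mentions no unequal-variance or robust option.

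The reasons given for the log transform are a "rightward skew that increases in severity with increasing treatment efficacy", a geometric mean closer to the median, a multiplicative effect of ezetimibe, and efficiency. Equal variance across arms is not among them.

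In Section 6.2 the three primary comparisons "will be tested simultaneously by a Hochberg procedure to control for multiple comparisons". Section 6.1 adds: "Two-sided tests of statistical significance will be used throughout".

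Section 6.5 sizes the trial on the arithmetic percentage scale with a single SD of 13%. It then says that further exploratory calculations, "based on logarithmic analysis and incorporation of an apparent increase in variation with increasing lipid-lowering effect", supported the result.

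**The concern.** An ordinary ANCOVA estimates one residual variance from all four arms and uses it for every pairwise contrast. Equal allocation protects a two-sample test against unequal variances. It does not protect a contrast whose error term is averaged with two arms outside the contrast.

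Write S40, S80, R10 and R20 for the simvastatin and rosuvastatin arms, all with ezetimibe. If variance rises with lowering, then by dose order within each drug R20 and S80 together have more variance than R10 and S40 together. The pooled standard error is then too small for R20 vs S80 and too large for R10 vs S40. These are two of the three confirmatory tests, and the two on which the trial was powered. Hochberg relies on valid p-values, and the reported confidence intervals carry the same distortion.

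**Working it through.** **The plan's own figure.** Inputs from Section 6.5: "it is reasonable to assume an effect size of approximately 5% for the 2 comparisons", SD 13 points, and "each of the 2 contrasts must have approximately 95% power". No alpha is stated; two-sided 5% is inferred from the 95% intervals. Then n = 2 × (1.96 + 1.645)² × 13²/5² = 175.7, so 176 per arm, and the t-based calculation gives 177. The stated 177 is reproduced. Two contrasts at 95% give 0.95² = 90%.

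**Assumed lowering.** The protocol gives no per-arm values. Taken here: S40 55%, R10 60%, S80 60%, R20 65%. This uses the 45% to 60% range in Section 1.1 for simvastatin/ezetimibe and the 5-point effect.

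**Log SDs.** With a 13-point SD in each arm and m the remaining fraction of baseline LDL-C, s² = ln(1 + (0.13/m)²):

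- S40, m = 0.45: s² = 0.0802, s = 0.283
- R10 and S80, m = 0.40: s² = 0.1004, s = 0.317
- R20, m = 0.35: s² = 0.1292, s = 0.359

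Pooled variance = (0.0802 + 2 × 0.1004 + 0.1292)/4 = 0.1026.

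**Standard errors.** Let k = √[(sₐ² + s_b²)/(2 × pooled)], the correct SE divided by the pooled SE.

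- R20 vs S80: k = √(0.2296/0.2052) = 1.058; the pooled SE is 5.5% too small.
- R10 vs S40: k = √(0.1806/0.2052) = 0.938; the pooled SE is 6.6% too large.
- R20 vs S40: k = 1.010; almost no effect.

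**Size of a nominal 5% contrast at a true null.** If SD depends on lowering, two arms with equal lowering have equal SDs. Size = 2(1 − Φ(1.96/k)), with lowering in the order S40/R10/S80/R20:

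- R20 = S80 at 55/60/60/60: pooled 0.0953, k = √(0.1004/0.0953) = 1.026, size 5.6%.
- R20 = S80 at 55/60/65/65: pooled 0.1098, k = √(0.1292/0.1098) = 1.085, size 7.1%.
- R10 = S40 at 55/55/60/60: pooled 0.0903, k = √(0.0802/0.0903) = 0.942, size 3.75%.
- R10 = S40 at 55/55/60/65: pooled 0.0975, k = √(0.0802/0.0975) = 0.907, size 3.1%.

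The SDs at 55/60/60/60 put R10 vs S40 at 4.4%, but R10 and S40 differ there, so this is a mild bound and not a null case.

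**Family-wise error through Hochberg** (simulated, 177 per arm, 13-point SD, pooled variance):

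| Lowering S40/R10/S80/R20 | True null(s) | Family-wise error |
|---|---|---|
| 55/60/60/60 | R20 = S80 | 5.1–5.2% |
| 52/57/60/60 | R20 = S80 | 6.2% |
| 50/55/60/60 | R20 = S80 | 6.6% |
| 55/60/65/65 | R20 = S80 | 6.9% |
| 55/57.5/60/60 | R20 = S80 | 4.1% |
| 55/55/60/60 | both | 4.7% |
| 55/55/60/65 | R10 = S40 | 3.0% |

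With separate variances the first four cases give 4.6% to 4.9%, and the last gives 4.9%.

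**Power for R10 vs S40** at 55/60/60/65. Difference ln(0.45/0.40) = 0.1178; own SE = √(0.1806/177) = 0.0319; pooled SE = √(2 × 0.1026/177) = 0.0340.

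- Own variance: Φ(0.1178/0.0319 − 1.96) = 95.8% (about 95.7% with t).
- Pooled: Φ((0.1178 − 1.96 × 0.0340)/0.0319) = 94.5%.

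Power for all three contrasts hardly moves: 91.4% pooled against 91.8% separate. The cruder conversion s = 0.13/m gives 89.6% against 90.0%.

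**The case against.** The strongest reply is that the protocol never says one residual variance will be used, and that variance structure is ordinarily settled in the SAP. That limits the claim to the model as ordinarily fitted. It does not remove it: Section 6.4 names the model and ties the p-values to it, while Section 6.5 reports a pattern that the default form of the model assumes away.

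Second, the evidence is thin. Section 6.5 calls the increase apparent, gives no per-arm SD, and does not say plainly on which scale it was seen. The remark on skew in Section 6.4 is not about variance, and a purely multiplicative effect would leave log variances equal. All of this stands as a limit on size. But equal log variances would make the percentage-scale SD fall as lowering increases. A constant or rising percentage-scale SD gives a rising log SD, so either reading of Section 6.5 points the same way.

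Third, Section 6.4 reports about 30% fewer subjects for the geometric analysis, and the log SDs used here show almost no such gain (95.8% against 95.0% at 177). The true log SDs may therefore be smaller. Only their ratios enter k, so a common rescaling changes nothing.

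Three stronger readings are tempting and not supported:

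- A reader might take 6.4%, the figure from k = 1.058 at 55/60/60/65, as the type I error for R20 vs S80 and assume that it passes in full into the family-wise error. It uses SDs from arms that differ in lowering. At true nulls the family-wise figure depends on the other contrasts and can lie below 5%.
- A reader might assume much steeper growth of the log SD per dose step. The documents give no rate.
- A reader might conclude that the arithmetic confidence intervals are also wrong. A constant 13-point SD makes the arithmetic variances equal, so this is not shown.

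**Conclusion.** The point holds as a modest inconsistency between planning and analysis. The mechanism and both directions follow from equal arms and variance that rises with lowering. The size rests on assumed lowering and on a 13-point SD in every arm: standard errors off by about 6%, and a true size of about 5.6% to 7% for R20 vs S80 and about 3% to 4.4% for R10 vs S40.

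Family-wise error runs from about 4.1% to 6.9% over the cases with only R20 = S80 null, and is about 3% where only R10 = S40 is null. The 6.9% case puts simvastatin 80 mg plus ezetimibe at 65%, above the range quoted in Section 1.1; with that arm at 60% the highest figure was 6.6%. If all arms lower LDL-C equally, nothing is distorted. The 177 per arm stands. The change is worth making, but the trial's validity does not depend on it.

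**What to change.** In Section 6.4, state that the log-ratio ANCOVA is fitted with a separate residual variance for each arm, using Satterthwaite or Kenward-Roger degrees of freedom, or with heteroscedasticity-robust standard errors. Take the three Hochberg p-values and the log-scale confidence intervals from that fit. Fix the choice before unblinding, so that the variance structure is not selected on the data.

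The cost is one sentence in the protocol or SAP, one option in the model code, and a negligible loss of degrees of freedom. Patients, visits and sample size do not change.

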3.5 Method of assigning patients to treatment groups

Once a patient has signed the written informed consent, they will be assigned with a unique identifying number (enrolment number). This enrolment number will be used as the identification number throughout the study and once allocated it will not be re-used. The enrolment number will be a combination of the site number and the sequential patient at that site.

Patient eligibility will be established before treatment randomisation. At Visit 3 (Week 0), patients who satisfy the entry criteria will be randomised by blinded randomisation via Interactive Voice Response System (IVRS) to receive either rosuvastatin monotherapy (10 mg or 20 mg) or simvastatin monotherapy (40 mg or 80 mg). After completion of monotherapy, patients will continue with the same dose of rosuvastatin or simvastatin but in combination with ezetimibe 10 mg. The randomisation scheme will be generated by an AstraZeneca representative using the GRand system. A blocked randomisation schedule by site will be produced for the main study. Patients will be randomised strictly sequentially as patients are eligible for randomisation. No one outside the group generating the randomisation scheme and the group adopting it in to the IVRS will have knowledge about the scheme. Hence, investigators will have no knowledge beforehand of the treatment the patient will receive.

If a patient discontinues from the study, the patient will not be allowed to re-enter the study.

If a patient is provided treatment by mistake which is not the treatment assigned by IVRS, no attempt should be made to remedy the error once study medication has been dispensed. The patient should continue with their original statin and dose, as provided, and from Visit 5 (Week 6) onwards in combination with ezetimibe. AstraZeneca or its representative should be notified as soon as the error is discovered.

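### The hs-CRP rank tests are valid but unadjusted for baseline hs-CRP and centre; adjusting, mainly for baseline, would gain power at almost no cost

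*Protocol*

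**What the plan says.** hs-CRP is one of the variables in secondary objective 2 (Section 2.2). The measure there is percentage change from baseline after six weeks of combination therapy, for the two rosuvastatin arms against the two simvastatin arms. Objectives 1 to 6 are formally tested if any primary component is significant.

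For the method, Section 6.4 states "Analysis of hs-CRP will be performed using the non-parametric Kruskal-Wallis test", then "The median score will be used" and "In the case of pairwise comparisons, a Wilcoxon test will be used". No covariate or stratum is named. The synopsis gives the same tests.

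Earlier in Section 6.4 the list of lipids and lipoproteins ends "TC/HDL-C, LDL-C/HDL-C, nonHDL-C/HDL-C and hs-CRP". The next paragraph but one sets out the general ANCOVA, in which "the response variable is the logarithm of the ratio of the treatment value divided by the corresponding baseline value". The model has two terms only: "treatment and centre are the explanatory variables". The synopsis version of the lipid ANCOVA adds baseline LDL-C.

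On allocation, Section 3.5 says "A blocked randomisation schedule by site will be produced for the main study".

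**The concern.** The baseline hs-CRP value has to be measured to form the change, so it is available at no cost, yet the test does not use it as a covariate. For a marker that varies within patients, change from baseline is correlated with baseline. An unadjusted test leaves that explainable variation in the noise. On the log scale it also passes a fraction (1 − ρ) of any chance baseline difference between arms into the contrast, where ρ is the correlation between baseline and on-treatment values. Centre defines the randomisation blocks and appears in both the ANCOVA and the logistic model of Section 6.4, but not in the hs-CRP tests.

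What is at stake is precision in every hs-CRP comparison. A smaller matter is wording: Section 6.4 lists hs-CRP just ahead of the ANCOVA paragraph and never says that it is excluded from that analysis.

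**Working it through.** **The protocol's own figure.** Section 6.5 requires 177 ITT patients per arm for LDL-C (difference 5%, SD 13%, 95% power per contrast). With two-sided α = 0.05 (assumed), n = 2 × (1.960 + 1.645)² × 13² / 5² = 175.7, so 176 by the normal approximation. With the t distribution, 177 per arm gives 95.04% power. The figure reproduces. It says nothing about hs-CRP, for which the protocol makes no power claim.

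**Inputs for hs-CRP.** From the protocol: about 177 patients per arm (or 200 × 0.9 = 180), two-sided tests, and allocation blocked by site. Assumed, because the protocol gives no values: log-normal hs-CRP with log SD 1 at both times, ρ = 0.5 to 0.8, and a true shift of 0.22 log SD.

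**Variances on the log scale.**
- Change from baseline: 2(1 − ρ).
- Adjusted for log baseline: 1 − ρ².
- Ratio, adjusted to unadjusted: (1 + ρ)/2, which is 0.75, 0.80, 0.85 and 0.90 for ρ = 0.5, 0.6, 0.7 and 0.8.
- The Wilcoxon test on normal data has a further relative efficiency of 3/π = 0.955.

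**Power by formula**, from z = 0.22 / √(variance × 2/177), power = Φ(z − 1.96), and z multiplied by √0.955 for Wilcoxon. Example at ρ = 0.5:
- Unadjusted log ratio: z = 0.22 / √(1 × 2/177) = 2.07, power 54.4%.
- Wilcoxon: z = 2.02, power 52.5%.
- Baseline-adjusted: z = 0.22 / √(0.75 × 2/177) = 2.39, power 66.6%.

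| ρ | Wilcoxon | Log ratio, no baseline | Log ratio + baseline |
|---|---|---|---|
| 0.5 | 52.5% | 54.4% | 66.6% |
| 0.6 | 61.8% | 63.8% | 73.5% |
| 0.7 | 74.2% | 76.2% | 82.6% |
| 0.8 | 89.2% | 90.5% | 93.2% |

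**Simulation of the same setting, adding a rank ANCOVA** (no site effects).

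| ρ | Wilcoxon | Rank ANCOVA | Log ratio, no baseline | Log ratio + baseline |
|---|---|---|---|---|
| 0.5 | 52% | 64% | 53% | 66% |
| 0.6 | 61% | 69% | 63% | 72% |
| 0.7 | 73% | 77% | 74% | 80% |
| 0.8 | 89% | 90% | 90% | 93% |

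Wilcoxon trails the rank ANCOVA by 12, 8, 4 and 1 points, and the baseline-adjusted log-ratio model by 14, 11, 7 and 4. It trails the log-ratio model without baseline by only 1 or 2.

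**Simulation with sites.** 180 per arm, 45 sites (assumed), blocked allocation, 1,500 runs per setting (Monte Carlo standard error about 1.2 points). The effect was set so that the fully adjusted model has about 80% power.

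| ρ | Site share of residual variance | Wilcoxon | Section 6.4 ANCOVA (treatment + centre) | The same + log baseline |
|---|---|---|---|---|
| 0.5 | 0% | 67.2% | 69.0% | 80.3% |
| 0.5 | 5% | 64.9% | 68.7% | 81.1% |
| 0.7 | 0% | 70.7% | 72.5% | 79.7% |
| 0.7 | 5% | 69.7% | 73.5% | 80.3% |

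Wilcoxon loses about 9 to 16 points against the fully adjusted model and 2 to 4 against the ANCOVA as written. A 5% site share lowers Wilcoxon power by 1.0 to 2.3 points, which is the basis for putting centre at about 0 to 3. Wilcoxon type I error was 4.3% to 5.0%.

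Over the two simulations, the loss is about 4 to 16 points against the baseline-adjusted log-ratio model. Moving to the Section 6.4 ANCOVA as written would recover about 1 to 4.

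**The case against.** The strongest reply is that nothing is wrong with the planned tests. Kruskal-Wallis and Wilcoxon are valid in a randomised comparison, the protocol claims no power for hs-CRP, and it is one secondary variable among many. That stands, and it limits the point to efficiency. It does not remove the point, because the protocol itself names the method in two places and the improvement needs no data.

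It can also be said that the size is wholly assumed: correlation, effect, number of sites and log-normality. That is correct. Log-normality favours the parametric model, and against a rank ANCOVA the gain falls to 1 point at ρ = 0.8.

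Four stronger readings are tempting, and the protocol does not support them.
- A reader might infer that baseline hs-CRP is ignored. It is not: the endpoint is percentage change from baseline, so baseline enters every ranked value. It is only not adjusted for.
- A reader might infer that chance baseline imbalance biases the result. Over randomisations it is already covered by the nominal error rate; adjustment reduces its influence in the trial at hand.
- A reader might infer that Section 6.4 sets two competing analyses. The hs-CRP sentence is specific, comes after the general list and matches the synopsis, so the rank tests naturally govern. What remains is a missing exclusion.
- A reader might infer that the loss comes from preferring ranks to the protocol's ANCOVA. As written in Section 6.4, that ANCOVA has no baseline term and performs almost like the Wilcoxon test.

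**Conclusion.** The point holds as a modest efficiency improvement on one secondary variable. The planned tests keep their type I error. Under log-normal data and ρ of 0.5 to 0.8 they give up about 4 to 16 power points against a log-ratio model with baseline hs-CRP, and about 1 to 12 against a rank ANCOVA. The loss shrinks as ρ rises. It is due almost entirely to the absent baseline covariate, with centre worth about 0 to 3 points. The protocol supplies none of the hs-CRP parameters, so these are ranges under stated assumptions.

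The sentence "The median score will be used" is unclear. If a reader took it to mean median scores in the rank test (relative efficiency 2/π = 0.64), power in the simulation with sites would be 45% to 52%. The protocol does not establish that reading, since it names Kruskal-Wallis and Wilcoxon and may simply mean the median as summary. That larger loss is therefore not part of this conclusion.

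**What to change.** In Section 6.4 and the synopsis, name one hs-CRP analysis that adjusts for baseline hs-CRP and (pooled) centre. A rank ANCOVA (Quade), extended to include centre, keeps the robustness to skewness. The log-ratio model with log baseline hs-CRP added is an alternative already close to the protocol's own method, but only one of the two should be named.

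Keep Kruskal-Wallis and Wilcoxon as sensitivity analyses and report medians descriptively. Say in so many words that the median is the summary statistic, if that is what is meant. In the Section 6.4 paragraph that lists the lipids and lipoproteins, state that hs-CRP is excluded from the general lipid ANCOVA.

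The baseline hs-CRP value also needs one definition. Section 6.4 averages Visits 2 and 3 and Section 4.6.2.1 has hs-CRP measured from Visit 1, whereas footnote d of Table 1 schedules it only from Visit 3.

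The cost is a wording change and a few lines of code, with no extra data. The small downside is that a rank ANCOVA is less familiar to readers than a Wilcoxon test.
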